### 7.5 Discharge, if different than 24 hours (-6/+12 hours)

If Subject is discharged in a time that is different than the 24 hours (-6/+12 hours),

the following data will be collected:

- Discharge status (for example, by CMS Patient Discharge Status Code)
- mRS Score- should be assessed by an independent clinician who is not a member of the investigational team.
- Complications and any AE's (including a determination of the severity, seriousness, and relationship to the device or procedure). These will specifically include stroke, hemorrhage and death.

- Antiplatelet and/or anti-coagulant Medications, if was changed from previous visit

#### **7.6 30 days ( $\pm$ 7 days), can be performed over the phone**

If an in-person visit cannot be performed, it is possible to perform via structured telephone interviews, with the exception of NIHSS.

30 days ( $\pm$  7 days) from time of procedure

- mRS Score- should be assessed by an independent clinician who is not a member of the investigational team.
- NIHSS
- Complications and any AE's (including a determination of the severity, seriousness, and relationship to the device or procedure). These will specifically include stroke, hemorrhage and death.
- Antiplatelet and/or anti-coagulant Medications, if was changed from previous visit

NIHSS will be performed by certified Study personnel.

#### **7.7 180 days ( $\pm$ 21 days)**

- mRS Score (If an in-person visit cannot be performed, it is possible to perform via structured telephone interviews)-should be assessed by an independent clinician who is not a member of the investigational team.
- Raymonds scale, using DSA
- Complications and any AE's (including a determination of the severity, seriousness, and relationship to the device or procedure). These will specifically include stroke, hemorrhage and death.
- Antiplatelet and/or anti-coagulant Medications, if was changed from previous visit

In some cases, this visit is also performed at 3 months ( $90 \pm 14$  days) as a standard of care, then the same information will be collected at 3 months as well.

Also note, if in-person visits are not possible, mRS assessments may be performed remotely by structured telephone interviews.

#### **7.8 Unscheduled Visits**

When clinically indicated, unscheduled assessments should be completed with corresponding data documented in the eCRF.

#### **7.9 Adverse Events**

Adverse events that occur during participation in the SUCCESS Study will be recorded. See section 11 for more information on AEs.

**Table 2: Schedule of Events**

Elapsed time/Study procedures	Baseline/Procedure	24 hours (-6/+12)	Discharge if different than 24 hours (-6/+12)	30 ( $\pm 7$ ) days	180 ( $\pm 21$ ) days**
Informed Consent	X				
Demographics	X				
Medical History and Concomitant Medications	X				
Brain CT Scan	X	X *			
Vital Signs	X				
mRS score +	X		X	X	X
NIHSS	X			X	
Clinical Laboratory	X				
Raymond scale	X***				X***
Intraoperative data	X				
Prior/concomitant medications	X	X	X	X	X
Adverse Events	X	X	X	X	X

(\*) If performed as a standard of care any time up to 24 hours post procedure

(\*\*) Will be collected if performed also at 90 ( $\pm 14$ ) days as a standard of care.

(\*\*\*) Post-procedure and 6 months imaging should use Digital Subtraction Angiography (DSA) for Raymond scale assessments.

(+) If in-person visits are not possible, mRS assessments may be performed remotely by structured telephone interviews.

## 7.10 Clinical Outcomes Assessment

Assessments to be performed as indicated in Table 2 are as follows:

**Modified Rankin Scale (mRS):** Measures the global degree of disability or dependence of an individual on an ordinal scale. Must be assessed by an independent clinician who is not a member of the investigational team, who is trained to conduct the mRS assessment. To the extent possible, the same examiner should examine all subjects at a single site.

## 8. STATISTICAL ANALYSIS-

### 8.1 General Principles

The detailed hypothesis generation and statistical method is provided below:

The primary effectiveness endpoint is successful intracranial aneurysm occlusion (measured by Raymond Roy classification I or II) at the end of procedure, using digital subtraction angiography (DSA).

The performance goal (PG) for evaluating effectiveness is based on outcomes as reported in the Comaneci de novo, which was successful aneurysm occlusion of 79.7% (51/64). The PG for the primary effectiveness is defined as success rate cited above minus a margin of 10%, therefore giving a PG of 69.7%.

The resulting null and alternative statistical hypotheses are as follows:

H0:  $p \leq PG$

HA:  $p > PG$

The hypothesis test will be performed at an overall two-sided alpha level of 0.05 using Chi-square test, in which the lower confidence bound on the observed incidence of success is compared to the PG.

With a hypothesized true incidence rate of 82.6% for successful intracranial aneurysm occlusion at the end of procedure and desired power of  $\geq 80\%$ , using a normal approximation test with a nominal 0.025 one-sided significance level (equivalent to a two-sided alpha=0.05), the required evaluable sample size for primary efficacy is 90 evaluable patients with a power of 80%.

The objective of this postmarket surveillance study is to reduce uncertainty regarding the safety profile of the device and its real-world performance. This objective will be met by capturing safety data as the device is used in practice by physicians in the United States. As specified by FDA's order to conduct a postmarket surveillance study under section 522 of the Federal Food, Drug and Cosmetic Act (the act), 21 U.S.C. 360l, a total N=120 deployed devices with complete 30 day post procedure patient status. This number of deployments was later adjusted and approved by the FDA to 90 in the current version of the protocol (version 2.0) as explained above. The focus of the study is to characterize the incidence and nature of periprocedural events occurring within 24 hours post-procedure as well as hospital discharge status and to characterize 30-day post-procedure status including 30-day functional status and all adverse events after discharge to day 30 for each use of the Comaneci Embolization Assist Device. Longer terms effectiveness at six months will be also descriptively summarized in terms of the Raymond scale and mRS.

Attempt to use the Comaneci device is defined as: in each IA case that may potentially require use of the Comaneci device where the sterile seal on the packaging was broken, whether or not the device is ever delivered to the target site of its intended use. The procedural case report form (CRF) will record all attempts to use the Comaneci device. All reasons the device may not have been used after the sterile seal

## SUCCESS Study

has been broken, including whether consent was obtained or not, will be provided.

Accounting for all unsealed Comaneci devices in each IA case that may potentially require use of the Comaneci device at a clinical site for the period of enrollment to the study will be provided: for devices unsealed and not used in the SUCCESS intent to treat (ITT) group described below, the accounts will not provide patient information but will provide some indication of the device disposition. There will be a separate CRF to track the disposition of all devices for which the sterile seal has been broken, including whether the device was used in a subject in the ITT group.

Any patient who is consented for endovascular treatment of an intracranial aneurysm (IA) that may potentially require use of the Comaneci device at the participating centers in the study, and a Comaneci device's package sterile seal was broken will form the basis of ITT. ITT patients that Comaneci device was not introduced to the body will be considered screen failure, and will not be followed up, but the reason for not introducing the Comaneci will be documented.

The primary safety endpoint analysis will be performed using the ITT population without screen failures.

All patients who meet all of the inclusion criteria and no exclusion criteria will form the basis for FAS primary analysis- for whom primary safety and efficacy analysis will be performed.

Descriptive summaries of the peri-operative and post-operative adverse events in both the ITT cohort and the FAS cohort will be reported.

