### **7.2.4 Screen Failures**

Subjects who were consented and not treated with the Comaneci device (device was not introduced to the body) due to not meeting the indication of the device, such as aneurysm size and anatomy, will be considered screen failures and will not be followed up, but the reason for not introducing the Comaneci will be documented. Screen failures will not be included in the primary safety endpoint analysis.

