## 8.2 Evaluation of Periprocedural Events

The rates of all adverse events occurring within 24 hours post procedure and hospital discharge status for all opened devices at each participating clinical site during the surveillance period will be summarized. Adverse events of special interest include vessel perforation or dissection, intracranial aneurysm rupture, stroke, hemorrhage, death, inability to deploy or remove the device, and coil entanglement. The numbers of individual adverse events of each type and the per subject incidence rate for each type of adverse event will be determined and reported along with 90% two-sided exact binomial confidence intervals. The upper bounds of 90% two-sided exact binomial confidence intervals are equivalent to the upper bounds of 95% one-sided exact binomial confidence intervals. While the estimated incidence rates for each type of adverse event will be taken as the most likely value of the true incidence rate, the corresponding upper bound of the one-sided 95% exact binomial confidence interval will be taken as the largest possible incidence rate consistent with the observed sample results.

Separate event counts and incidence rates with corresponding confidence intervals will be summarized for adverse events determined to be serious, device-related, serious and device-related, procedure-related, serious and procedure-related, and severe. Listings for all adverse events will be compiled that provide full descriptions of each adverse event including determination of the severity, seriousness, and relationship to the device or procedure. The following listings will be compiled:

- AE Listing 1 All AEs Sorted by Event Type
- AE Listing 2 All AEs Sorted by Subject and Relative Time of Onset
- AE Listing 3 Serious AEs
- AE Listing 4 Severe AEs
- AE Listing 5 Device-Related AEs
- AE Listing 6 Procedure-Related AEs
- AE Listing 7 Serious Device or Procedure Related AEs
- AE Listing 8 Severe Device or Procedure Related AEs

Discharge status will be described with counts and percentages.

Evaluation of the extent of any relationship between adverse event rate to operator experience will be evaluated. Operator experience will be evaluated by credentialing the investigators by years of training, number of aneurysms treated endovascularly in the last two years.

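### The plan contradicts itself on whether an opened device that fails before entering the body counts as inability to deploy, so the primary rate of that event can be too low

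*Combined protocol and SAP*

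**What the plan says.** **The event.** Section 3.1 places inability to deploy or remove the device among the periprocedural safety events. Section 7.3.2 collects it during the procedure. Section 8.2 repeats it: "Adverse events of special interest include vessel perforation or dissection, intracranial aneurysm rupture, stroke, hemorrhage, death, inability to deploy or remove the device". Each event type gets a per-subject incidence with a 90% two-sided exact binomial interval. Nowhere is inability to deploy defined, and no text says whether it covers failure before the device enters the body.

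**The attempt and the base for rates.** Section 8.1 starts an attempt when the sterile seal is broken, "whether or not the device is ever delivered to the target site of its intended use". Section 8.2, like the Statistical Analysis entry of the Protocol Summary, takes opened devices as the base for periprocedural event rates.

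**The exclusion.** Section 8.1 builds the ITT group on consent plus a broken seal, then states that "ITT patients that Comaneci device was not introduced to the body will be considered screen failure". No reason is required. It continues: "The primary safety endpoint analysis will be performed using the ITT population without screen failures". Section 7.2.4 agrees that "Screen failures will not be included in the primary safety endpoint analysis", but its own definition is narrower. There, non-introductions "due to not meeting the indication of the device, such as aneurysm size and anatomy, will be considered screen failures".

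**Other sets.** Section 8.1 also says "All patients who meet all of the inclusion criteria and no exclusion criteria will form the basis for FAS primary analysis", and assigns primary safety and efficacy to that set. It promises descriptive adverse event summaries in both the ITT and FAS cohorts.

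**The concern.** A device that is opened but cannot be prepared, loaded or expanded on the table is an attempt under the plan's own definition. Under the Section 8.1 screen-failure rule the same case leaves the primary safety analysis because the device did not get as far as the body. If such a case belongs under inability to deploy, exclusion from the rate depends on the outcome that the rate is meant to measure.

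Two analysts could follow the document faithfully and report different rates. One, using Section 8.1, could report zero when devices had failed. The other, using Section 8.2 or the Section 7.2.4 definition, would count them.

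This matters because of how the interval will be read. Section 8.2 treats the one-sided 95% upper bound as the highest incidence compatible with the data. That reading fails if the earliest failures were removed before the bound was computed.

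**Working it through.** **No planned figure on this point.** The documents state no expected device-failure rate, no number of screen failures and no number of devices opened but not introduced. The only computed design figure is the 90 evaluable patients of Section 8.1. It reproduces:

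- n = [1.960 × √(0.697 × 0.303) + 0.842 × √(0.826 × 0.174)]² / (0.826 − 0.697)² = 89.4, so 90. Power at 90 is 80.3%.

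That figure concerns occlusion. Here 90 serves only as an illustrative number of subjects in whom the device was introduced.

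**Passages side by side**, for a consented subject whose opened device fails before body entry:

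| Text | Treatment of the case |
|---|---|
| 8.1, attempt | Counts: seal broken |
| 8.1, screen failure | Screen failure, whatever the reason |
| 8.1, primary safety on ITT without screen failures | Out of numerator and denominator |
| 7.2.4 | Not a screen failure if the indication was met |
| 8.2 and Protocol Summary | In the base: device opened |
| 8.1, FAS sentence | Not excluded by that sentence if the criteria are met |
| 8.1, descriptive ITT summary | Not stated whether screen failures are in |
| 6.2 against 5.1.1 | Not enrolled without an attempt to introduce through the arterial sheath, against enrolled at consent |

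**Size, as an illustration.** Let x be in-body failures among 90, k the subjects with an opened device not introduced, and m those of the k who had a device failure. The rate is x/90 with the exclusion and (x + m)/(90 + k) without it. The upper bound is the 0.95 quantile of Beta(events + 1, n − events). For 0/90 it is 1 − 0.05^(1/90) = 3.3%.

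If every excluded case is a device failure (m = k, an assumption):

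| m = k | Starting from x = 0: rate (upper bound) | Starting from x = 2: rate (upper bound) |
|---|---|---|
| 0 | 0/90 = 0.0% (3.3%) | 2/90 = 2.2% (6.8%) |
| 1 | 1/91 = 1.1% (5.1%) | 3/91 = 3.3% (8.3%) |
| 2 | 2/92 = 2.2% (6.7%) | 4/92 = 4.3% (9.7%) |
| 3 | 3/93 = 3.2% (8.1%) | 5/93 = 5.4% (11.0%) |
| 5 | 5/95 = 5.3% (10.8%) | 7/95 = 7.4% (13.4%) |

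Each omitted failure is worth about 1.1 percentage points. With none observed in the body, two omitted failures halve the upper bound that would otherwise be reported (3.3% against 6.7%).

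**Direction.** (x + m)/(90 + k) exceeds x/90 exactly when m/k exceeds x/90. If none of the excluded cases is a device failure (m = 0, k = 5, x = 2), inclusion moves 2/90 = 2.2% to 2/95 = 2.1%, so exclusion slightly raises the rate.

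**The case against.** A reader might infer that the reported device-failure rate will be too low, and that this holds whichever analysis set leads. The documents do not support that, for these reasons:

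- **Base in Section 8.2.** Opened devices are the stated base there, just before the event is listed. This stands, and it makes the defect a contradiction rather than one settled rule. It does not remove the problem: Section 8.2 gives a per-subject rate without stating its denominator, and Section 8.1 still takes these subjects out of primary safety.
- **Narrower rule in Section 7.2.4.** A device that fails on the table does not fit a definition based on the indication. This stands too, and leaves two definitions of the same term.
- **ITT summaries and FAS.** The exclusion is tied to ITT without screen failures, while the FAS sentence does not require introduction. Independence from the analysis set therefore cannot be claimed. But Section 7.2.4 excludes screen failures from primary safety without naming a set, and Section 8.1 does not say whether its ITT summaries include them.
- **Undefined event.** Inability to deploy may have been meant for in-body failure only. Section 7.3.2 lists it with intraprocedural complications, and Section 4 describes the core wire as sizing the device in the target vessel. Section 11.2.1 defines an adverse event as an untoward medical occurrence, so a harmless table-side malfunction might never be recorded as one. All this is fair, and it is why the event needs a definition.
- **Second device.** The Section 8.1 rule can be read as reaching only patients in whom no Comaneci device was introduced. A table-side failure followed by a second, introduced device would then keep the subject in the set.
- **The cases are recorded.** Attempts, reasons for non-use and the disposition of every opened device go on CRFs, and malfunctions are reported under Section 11.4. This stands, but no rate is specified from those records.

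**Conclusion.** The plan gives conflicting instructions on whether a device failure between seal break and body entry counts toward inability to deploy. If the Section 8.1 screen-failure rule is applied as written, and such failures are regarded as part of the event, they leave numerator and denominator and the primary rate can be too low.

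How far cannot be computed, because the number of such cases is not given. On the assumption of 90 subjects with an introduced device, no in-body failure and two pre-entry failures in other subjects, the report would read 0% (upper bound 3.3%) where 2/92 = 2.2% (6.7%) would otherwise be shown.

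Downward bias is not certain. It requires that the share of device failures among the non-introduced cases exceed the rate among the introduced ones; non-introductions for anatomy work slightly the other way. The point should be settled before analysis, since the choice of denominator could otherwise be made with the counts in view.

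**What to change.** **Section 8.1.** Align the screen-failure rule with Section 7.2.4, so that non-introduction because of a device or preparation problem is not a screen failure for this event.

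**Section 8.2.** State that inability to deploy includes device failures after the seal is broken and before body entry. Report it with the exact 90% interval over all consented broken-seal ITT subjects. Show pre-entry and post-entry failures on separate lines. Non-introductions for anatomy or indication stay in the denominator but are not counted as events; the separate lines keep their diluting effect visible.

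**Other adverse event rates.** Reconcile the denominators of Sections 8.1 and 8.2 without narrowing the opened-device base of Section 8.2 by default. Reconcile the enrolment definitions in Sections 5.1.1 and 6.2 at the same time, since they decide whether such a case is enrolled at all.

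**Cost.** A few sentences and one added table line. The procedural CRF already records attempts and reasons for non-use, and the disposition CRF covers every opened device. The event is known at the procedure, so counting it needs no follow-up data. The downside is that the reported failure rate may look slightly worse.

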## 8.2 Evaluation of Periprocedural Events

The rates of all adverse events occurring within 24 hours post procedure and hospital discharge status for all opened devices at each participating clinical site during the surveillance period will be summarized. Adverse events of special interest include vessel perforation or dissection, intracranial aneurysm rupture, stroke, hemorrhage, death, inability to deploy or remove the device, and coil entanglement. The numbers of individual adverse events of each type and the per subject incidence rate for each type of adverse event will be determined and reported along with 90% two-sided exact binomial confidence intervals. The upper bounds of 90% two-sided exact binomial confidence intervals are equivalent to the upper bounds of 95% one-sided exact binomial confidence intervals. While the estimated incidence rates for each type of adverse event will be taken as the most likely value of the true incidence rate, the corresponding upper bound of the one-sided 95% exact binomial confidence interval will be taken as the largest possible incidence rate consistent with the observed sample results.

Separate event counts and incidence rates with corresponding confidence intervals will be summarized for adverse events determined to be serious, device-related, serious and device-related, procedure-related, serious and procedure-related, and severe. Listings for all adverse events will be compiled that provide full descriptions of each adverse event including determination of the severity, seriousness, and relationship to the device or procedure. The following listings will be compiled:

- AE Listing 1 All AEs Sorted by Event Type
- AE Listing 2 All AEs Sorted by Subject and Relative Time of Onset
- AE Listing 3 Serious AEs
- AE Listing 4 Severe AEs
- AE Listing 5 Device-Related AEs
- AE Listing 6 Procedure-Related AEs
- AE Listing 7 Serious Device or Procedure Related AEs
- AE Listing 8 Severe Device or Procedure Related AEs

Discharge status will be described with counts and percentages.

Evaluation of the extent of any relationship between adverse event rate to operator experience will be evaluated. Operator experience will be evaluated by credentialing the investigators by years of training, number of aneurysms treated endovascularly in the last two years.

In addition, Successful intracranial aneurysm occlusion (measured by Raymond Roy classification I or II) at the end of procedure will be descriptively summarized in terms of the number and percentage of subjects.

### **8.3 30-day post-procedure status**

30-day functional status will be assessed using the modified Rankin Scale (mRS). This scale runs from 0-6, from no symptoms to death as follows:

- 0 - No symptoms
- 1 - No significant disability. Able to carry out all usual activities, despite some symptoms.
- 2 - Slight disability. Able to look after own affairs without assistance, but unable to carry out all previous activities.
- 3 - Moderate disability. Requires some help, but able to walk unassisted.
- 4 - Moderately severe disability. Unable to attend to own bodily needs without assistance, and unable to walk unassisted.
- 5 - Severe disability. Requires constant nursing care and attention, bedridden, incontinent.
- 6 - Dead.

The frequency distribution and cumulative frequency distribution of the 30-day mRS will be summarized using counts and percentages.

All adverse events after discharge (device-related and non device-related) for each use of the Comaneci Embolization Assist Device will be summarized similarly to how periprocedural events will be summarized as described above. This includes counts, per subject incidence rate, exact binomial confidence intervals, and a separate set of adverse event listings that contain full descriptions of each adverse event including determination of the severity, seriousness, and relationship to the device or procedure.

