Statistical Analysis	
The rates of all adverse events occurring within 24 hours post procedure, hospital discharge status and after discharge for all opened devices at each participating clinical site during the surveillance period will be summarized. The numbers of individual adverse events of each type and the per subject incidence rate for each type of adverse event will be determined and reported along with 90% two-sided exact binomial confidence intervals. Separate event counts and incidence rates with corresponding confidence intervals will be summarized for adverse events determined to be serious, device-related, serious and device-related, procedure-related, serious and procedure-related, and severe. Listings for all adverse events will be compiled that provide full descriptions of each adverse event including determination of the severity, seriousness, and relationship to the device or procedure. Discharge status will be described with counts and percentages.
 
Effectiveness at six months will be descriptively summarized in terms of the number and percentage of subjects achieving successful aneurysm occlusion measured by Raymond scale grade I and II and by clinical outcome as measured by mRS shift analysis comparing preprocedure mRS (up to 24 h prior to treatment) with 6 month mRS. In addition, tetrachotomized (0,1, 2, 3-6) mRS analysis will also be performed. mRS will also be evaluated at discharge and 30 days. Successful aneurysm occlusion will also be evaluated at the end of procedure. Stability of occlusion will be evaluated by comparing the two angiographic studies that are 6 months apart. The distribution of scores will be summarized by counts and percentages. If only three month Raymond scale value is available but not the six month, the three month value will be used in these analyses. Similarly, the last available earlier mRS values will be used if the six month value is not available.

-----------------------------	--

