### 3.1 Endpoints

#### Safety

- Periprocedural events\*: Rates of all adverse events occurring within 24 hours post-procedure and hospital discharge status.
- All adverse events at discharge and up to 30 days post procedure.
- Functional status at discharge and 30-days assessed using the modified Rankin Scale (mRS).

**Secondary safety endpoint:** evaluation of the extent of any relationship between adverse event rate to operator experience

(\* ) Including vessel perforation or dissection, intracranial aneurysm rupture, stroke, hemorrhage, death, inability to deploy or remove the device, and coil entanglement

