### **7.2.3 Pre- Treatment Data:**

- Aneurysm size and location
- Pre-procedure mRS score (modified Rankin Scale)-up to 24h prior to treatment.
- Pre symptoms mRS
- NIHSS
- Pre op antiplatelet and/or coagulation medications

NIHSS will be performed by certified Study personnel.

mRS will be assessed by an independent clinician who is not a member of the investigational team.

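### Discharge and 30-day mRS are safety endpoints, but no planned summary sets them against the pre-procedure mRS or splits them by rupture status, so disability already present is mixed with new decline

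*Combined protocol and SAP*

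**What the plan says.** Section 3.1 lists among the safety endpoints "Functional status at discharge and 30-days assessed using the modified Rankin Scale (mRS"). Section 8.1 makes 30-day functional status part of the study's stated focus.

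- **30 days.** Section 8.3 gives one analysis of the score: "The frequency distribution and cumulative frequency distribution of the 30-day mRS will be summarized using counts and percentages". It mentions no baseline value, interval or subgroup.
- **Discharge.** Section 8 names no mRS analysis. Section 8.2 says "Discharge status will be described with counts and percentages", but section 7.5 lists that item separately from mRS, as a disposition: "Discharge status (for example, by CMS Patient Discharge Status Code"). The synopsis adds only "mRS will also be evaluated at discharge and 30 days" and, in general terms, "The distribution of scores will be summarized by counts and percentages".
- **Baseline.** Section 7.2.3 collects "Pre-procedure mRS score (modified Rankin Scale)-up to 24h prior to treatment", and also an mRS from before symptoms. The only analysis that uses a baseline score is at six months, under effectiveness: "mRS shift analysis comparing preprocedure mRS (up to 24 h prior to treatment) with 6 month mRS". No analysis is named for the pre-symptom score.
- **Rupture status.** Section 6.2.1 admits both ruptured and unruptured aneurysms. The subgroup analysis in section 8.5 covers selected adverse event rates and does not mention mRS.

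**The concern.** A distribution of scores after treatment describes where patients ended up. It does not show how many declined. That matters here because the study pools patients whose starting points can differ widely: section 1.1 says that two-thirds of patients with aneurysm rupture die or are left with a disabling deficit, while an unruptured aneurysm may be treated electively. A pooled 30-day table therefore reflects the ruptured/unruptured mix as well as any effect of the procedure.

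The plan already reads mRS against its pre-procedure value at six months, for efficacy. It does not do so at the two visits where mRS is a safety endpoint, although section 8.1 gives the study's objective as reducing uncertainty about the safety profile. A reader of the final report could not tell from the mRS tables whether a given share at mRS 3-6 was there before treatment.

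**Working it through.** **The plan's own figure.** The only calculated design figure is the 90 evaluable patients for end-of-procedure occlusion (section 8.1). With p0 = 0.697, p1 = 0.826, one-sided 0.025 and 80% power:

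n = [(1.960 × √(0.697 × 0.303) + 0.842 × √(0.826 × 0.174)) / (0.826 − 0.697)]² = 89.4, rounded up to 90.

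It reproduces. This point does not depend on it; 90 serves below only as the denominator.

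**What the 30-day distribution can and cannot fix.** Let N = 90, let b be the number at mRS 3-6 before the procedure and k the number at mRS 3-6 at 30 days. The number who moved from 0-2 to 3-6 lies between max(0, k − b) and min(k, N − b). The documents give neither b nor k, so these are assumed values:

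| k at 30 days | b before procedure | newly at 3-6 |
|---|---|---|
| 18 (20%) | 0 | exactly 18 (20%) |
| 18 (20%) | 9 | 9 to 18 (10% to 20%) |
| 18 (20%) | 18 | 0 to 18 (0% to 20%) |
| 9 (10%) | 9 | 0 to 9 (0% to 10%) |
| 27 (30%) | 27 | 0 to 27 (0% to 30%) |

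The planned table reports k only. Adding b as a second marginal table would narrow the range but in general not close it. Only the paired table gives the number.

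**An illustration by rupture status, on assumed inputs.** Suppose 40% of the 90 are ruptured (36) and half of those (18) are at mRS 3 or more before treatment and stay there.

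- No new decline: 18/90 = 20.0% at mRS 3-6 at 30 days (90% exact interval 13.3% to 28.2%).
- Five unruptured subjects go from 0 to 3: (18 + 5)/90 = 25.6%, which is inside that interval.
- Among the 90 − 36 = 54 unruptured subjects the same five are 5/54 = 9.3% (90% exact interval 3.7% to 18.5%).

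Varying the assumed ruptured share, still with half of the ruptured subjects at mRS 3 or more:

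| ruptured share | at 3-6, no decline | at 3-6, five unruptured decline | five among unruptured |
|---|---|---|---|
| 20% (18) | 9/90 = 10.0% | 14/90 = 15.6% | 5/72 = 6.9% |
| 40% (36) | 18/90 = 20.0% | 23/90 = 25.6% | 5/54 = 9.3% |
| 60% (54) | 27/90 = 30.0% | 32/90 = 35.6% | 5/36 = 13.9% |

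Under these assumptions, moving the ruptured share by 20 points shifts the pooled figure by 10 points, while the five declines shift it by 5/90 = 5.6 points.

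**The case against.** **The analysis matches the endpoint.** Section 3.1 names functional status, not change in status, and a frequency table describes status. This is fair: the plan is not inconsistent here. The point is that a more informative summary is available from a score already on the schedule.

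**Harm is captured elsewhere.** A reader might infer that the study cannot detect harm from the procedure, or leaves the safety question unanswered. The documents do not support that. Stroke, haemorrhage and death are specifically collected at 24 hours, discharge and 30 days with severity, seriousness and relatedness (7.4 to 7.6). Worsening of a prior condition counts as an adverse event (11.2.1). The DSMB adjudicates the relatedness of all SAEs (11.3). Rates carry 90% exact intervals and full listings (8.2), and selected rates are split by rupture status (8.5). The five declining subjects in the illustration should appear there. What remains is narrower: these sources rest on event reporting and attribution and do not give change in function, whereas mRS is scored by an independent clinician outside the investigational team (7.10).

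**The synopsis may already extend the shift analysis to the earlier visits.** The sentence on discharge and 30 days follows the description of the six-month analyses, so that reading is possible. It states no comparison, however, and section 8.3, the specific text for 30 days, has none.

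**A shift table would not isolate procedural harm.** This stands for ruptured subjects. In a single-arm study their change mixes the procedure with the course of the haemorrhage, and recovery can mask harm.

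**The baseline may be weak where it matters most.** This also stands in part. Ruptured subjects may consent up to 72 hours after the procedure, and nothing enters the eCRF before consent (5.1.1), so some pre-procedure scores may be missing or assigned afterwards.

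**Conclusion.** The point holds as a limit of the planned mRS summaries. No section plans a comparison of discharge or 30-day mRS with the pre-procedure score or a split of mRS by rupture status, and section 8 specifies no discharge mRS analysis. The tables as planned cannot separate disability present before treatment from new decline. It is not a failure of the safety evaluation as a whole, because adverse event reporting covers harm by another route.

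The size cannot be fixed from the documents, which give neither the ruptured fraction nor a baseline mRS distribution. The range of 0 to 18 newly dependent subjects, and the 20%, 25.6% and 9.3% figures, illustrate the mechanism on assumed inputs. They do not predict what the study will find. No test, decision rule or sample size rests on this descriptive endpoint.

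**What to change.** In section 8.3:

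1. Add a cross-tabulation of pre-procedure mRS by discharge mRS and by 30-day mRS, separately for ruptured and unruptured subjects. This would also give discharge mRS a stated analysis.
2. From it, report the number and percentage who worsened, for example by at least 1 point and by at least 2 points, or who died, with the 90% exact binomial intervals already used for safety in section 8.2.
3. Keep the frequency and cumulative distributions as a second table.
4. Report how many subjects have both scores at each visit, and how many pre-procedure scores are missing or were assigned retrospectively, by rupture status.
5. State that in ruptured subjects the shift does not separate procedural harm from the course of the haemorrhage, so the unruptured group is the more interpretable one.

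The cost is SAP wording and one table from scores already on the schedule, plus a record of when the pre-procedure score was assigned if the eCRF does not already hold it. Sample size, alpha and power do not change.
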